4.3 Study Subjects

4.3.1 Disposition of Subjects

A clear accounting of the disposition of all subjects who enter the study from screening to study completion will be generated.

The following summaries will be generated.

- A summary of subjects with informed consents, screen failure subjects by reasons, subjects randomized, entering and discontinuing each period (week 1-8, week 9-104 and post-treatment), subjects completed the study and discontinued subjects (Analysis population: all subjects with informed consents)
- A summary of the number of subjects randomized per site and per country/region (Analysis population: all subjects randomized)
- A summary of subjects treated (with at least one IMP administration), subjects completed the study and discontinuations from the study with major reasons. (Analysis population: all subjects randomized)

4.3.2 Protocol Deviations

The protocol deviation summaries may include the following:

- A summary of subjects with major protocol deviation in each country/region and site by treatment arm and overall and by type of deviation (Analysis population: all subjects randomized)
- A summary of the number and percentage of subjects with major deviations (Inclusion/Exclusion Criteria, Withdrawal Criteria, IP administration/Study treatment, Disallowed Medication)
- A by-subject listing of major or minor protocol deviations will be generated.

4.4 Analysis Populations

In this study, 4 analysis populations are employed, and the definitions are described in the following section. The analysis population summaries include the following:

- A summary of the number and percentage of subjects by treatment arm for each analysis population will be generated.
- A by-subject listing of analysis population details (site, subject ID inclusion/exclusion flag for each population and reason for exclusion from each population) will also be generated.

4.4.1 Safety Analysis Set

The safety analysis set (SS) includes all subjects who have received the IMP at least once and from whom data on at least one safety endpoint was obtained after the start of IMP administration.

If subjects have received the wrong IMP administration other than the one that they were originally randomized into, then they will be analyzed as “As treated”.

4.4.2 Full Analysis Set

The full analysis set (FAS) includes all subjects who received the IMP at least once and from whom data on at least one efficacy endpoint was obtained after the start of IMP administration.

If the subjects receive the wrong IMP administration, then they will be analyzed as “As randomized”.

4.4.3 Per Protocol Set

The per protocol set (PPS) includes all FAS subjects except those who have major protocol deviations or those who have withdrawn from the trial within 8 weeks from start of IMP administration. However, if a subject withdrew due to any reason other than an event (relapse or death) within 8 weeks from start of IMP administration, the subject will still be included in the PPS.

Subjects with the following major protocol deviations are excluded from PPS.

- Inclusion/Exclusion Criteria
- Compliance deviations (Patients do not receive the IMP at least 2 times up to the 8th administration or compliance rate is less than 80% throughout the period.)
- Disallowed medications
- Withdrawal Criteria

If the subjects receive the wrong IMP administration, then they will be analyzed as “As randomized”.

4.4.4 Immune Response Set

The immune response set (IRS) includes all subjects who received the IMP at least once and from whom data on at least one immune response endpoint were obtained after the start of IMP administration.

If the subjects receive the wrong IMP administration, then they will be analyzed as “As treated”.

4.5 Demographic and Other Baseline Characteristics

1) Definition:

Demographic:

Age, sex, height, body weight (at screen), race, trial country/region

Age will be divided into 3 groups (60 to 64 years, 65 to 70 years, ≥ 71 years).

Underlying diseases, induction/consolidation therapy and other baseline factors

Diagnosis of AML (WHO classification), duration from the last dose of consolidation therapy to randomization, duration from diagnosis of AML to randomization, regimen of number and therapy (induction, consolidation), WT1 mRNA level at Day 1, unfavorable karyotype abnormality (abn(3q)/inv(3)/t(3;3) or -5/del(5q) or -7/del(7q) or t(6;9)), cytogenetic abnormality (FLT3-ITD mutation)

WT1 mRNA level (copy/ugRNA) will be divided into 4 categories (<50, 50-199, 200<= and Unknown).

Prior and concomitant drugs/treatments

Prior and concomitant medications will be classified by Anatomic Therapeutic Chemical Classification 2 (ATC2) and generic (preferred) name using World Health Organization Drug Dictionary (WHO-DD).

The start or stop dates of administration of drugs/treatments other than IMP will be compared to the date of first IMP administration to classify them as either prior or concomitant drugs/treatments.

Table 4.5-1 Prior and Concomitant Drugs/Treatments	
Prior	Stop date of drug/treatment \leq First IMP administration date
Concomitant	Stop date of drug/treatment $>$ First IMP administration date

Concomitant drugs/treatments starting after the completion/withdrawal date will be listed but will not be classified or summarized.

Medical history and Concomitant disease

Medical history and concomitant disease are coded using Medical Dictionary for Regulatory Activities (MedDRA version 20.1). If the condition is not continuing at the

time of informed consent, it is considered as medical history. If the condition is continuing, then it is concomitant disease.

2) Analysis Set:

FAS, PPS, SS, IRS

3) Analysis Method:

Frequency counts and percentage or descriptive statistics for each variable will be calculated according to the nature of the data (continuous or discrete) by treatment arm and overall. For WT1 mRNA level, the measurement “<50” will be translated into 49 when calculating descriptive statistics.

The following summaries will be generated.

- A summary of demographic variables at baseline by treatment arm and over all
- A summary of other baseline characteristics by treatment arm and overall
- Subgroup analysis (Age, Country/Region) of demographic characteristics (FAS only)
- Subgroup analysis (Age, Country/Region) of other baseline characteristics (FAS only)
- A summary of prior and concomitant drugs/treatments (WHO drug terms) by treatment arm and overall (FAS only)
- A summary of Medical history by System Organ Class (SOC) and Preferred Term (PT) by treatment arm and overall (FAS only)
- A summary of Concomitant disease by SOC and PT by treatment arm and overall (FAS only)

4.6 Treatment Compliance

1) Definition:

- Treatment compliance will be calculated as

$$Treatment\ compliance(\%) = \frac{Actual\ number\ of\ IMP}{Scheduled\ number\ of\ IMP} \times 100,$$

Where the scheduled number of IMP administrations is the number scheduled until the time of withdrawal.

2) Analysis Set:

SS

3) Analysis Method:

A summary of the descriptive statistics will be calculated by treatment arm. Compliance rates (%) will be divided into 6 categories (<20, 20 - <40, 40 - <60, 60 - <80, 80 - <100, 100). The following outputs will be generated.

- A summary of IMP exposure by compliance rate
- A by-subject listing of treatment compliance data

4.7 Efficacy Evaluation

FAS will be used as the primary analysis population and PPS will be used as the secondary analysis population to evaluate the stability.

4.7.1 Primary Efficacy Endpoints

4.7.1.1 Disease-free Survival

1) Definition:

- Observation period: For each subject, the time from randomization to the DFS-cutoff date. The DFS-cutoff date was set as the completion/discontinuation date of each subject.
- DFS: The time from randomization until relapse or death from any cause, whichever comes first by the DFS-cutoff date.
- Event: Relapse or death from any cause by the DFS-cutoff date.
- Censoring:
 - If an event has not been observed by the DFS-cutoff date, then the last confirmed non-relapse date will be used as the censoring date.
 - For subjects who have withdrawn from this trial before the completion date for reasons other than relapses or deaths, if non-relapse has been confirmed on the withdrawal date, then the withdrawal date will be used as the censoring date. Otherwise, the last confirmed non-relapse date will be used as the censoring date.

2) Analysis Set:

FAS (primary), PPS

For the judgment of relapse by the central pathological review committee, DFS will be evaluated in the FAS and PPS as primary analysis.

For the judgment of relapse by trial site, DFS will only be evaluated in the FAS as secondary analysis.

3) Analysis Method:

- Primary test for comparison between OCV-501 and Placebo will be conducted by Log-rank test. For exploratory purposes, the Harrington-Fleming (HF) test will be performed by applying the weight $1 - \hat{S}(t)$, where $\hat{S}(t)$ is the product-limit estimates of survival functions.
- Kaplan-Meier estimate of survivor function $\hat{S}(t)$ and curve

$$\hat{S}(t) = \Pr(\text{Survive beyond } t)$$
$$= \prod_{j: t_j < t} \left(\frac{n_j - y_j}{n_j} \right)$$

where t_j is the j -th event time, n_j is the number of patients at risk and y_j is the number of events.

The Kaplan-Meier curve plots the estimated survival function $\hat{S}(t)$ vs. time separately for each treatment arm.

- The 2-year survival rate and median survival time will be calculated. The 95% CI of the 2-year survival rate will be calculated using Greenwood formula.
- Hazard ratio (HR) and its 95% CI will be calculated from the Cox proportional hazards model.
 - In the model of Cox analysis, treatments effect will be adjusted with covariates (Age, Country/Region and WT1 mRNA level at Day 1). The model with covariates (WT1 mRNA only) or model without covariates will be also analyzed. In these models, age will be categorized into 3 groups (60 to 64 years, 65 to 70 years, ≥ 71 years), Country/Region into 2 groups (Japan, Republic of Korea+Taiwan), WT1 mRNA into 4 groups (<50, 50-199, 200<= and Unknown).
 - BRESLOW method will be used for ties.
 - Proportionality assumption in Cox proportional hazard model will be assessed using 2 methods:
 - 1) SAS PHREG procedure ASSESS PH option will be used for checking proportional hazard assumption.
 - 2) Look at the log-minus-log survival plots graphically. If the graph results in parallel lines then the proportionality assumption is satisfied.
- HR and its 95% CI at every 3 months interval will be calculated by adding a time varying covariate to Cox Proportional Hazards model as an alternative analysis if the proportionality assumption fails. The model will be as follows:

$$\lambda(t;X) = \lambda_0(t) \exp(\beta_1 \text{trt} * \text{period}_1 + \beta_2 \text{trt} * \text{period}_2 + \dots)$$

where $\lambda_0(t)$ is the baseline hazard function,

trt is the treatment arm(1= OCV-501 and 0= Placebo) and

$$period_1 = \begin{cases} 1 & \text{if } 0 \leq DFS \text{ time} < 3 \text{ Months} \\ 0 & \text{otherwise} \end{cases}$$

$$period_2 = \begin{cases} 1 & \text{if } 3 \leq DFS \text{ time} < 6 \text{ Months} \\ 0 & \text{otherwise} \end{cases}$$

...

So HR (OCV-501 vs. Placebo) for each period will be calculated as follows:

$$\lambda(\text{OCV-501}|\text{period}_k) = \lambda_0(t)\exp(\beta_k)$$

$$\lambda(\text{Placebo}|\text{period}_k) = \lambda_0(t)$$

$$\text{HR}(\text{OCV-501 vs. placebo}|\text{period}_k) = \lambda_0(t)\exp(\beta_k) / \lambda_0(t) = \exp(\beta_k)$$

$$95\% \text{ CI} : [\exp(\beta_k - 1.96 * \sqrt{\text{Var}(\beta_k)}), \exp(\beta_k + 1.96 * \sqrt{\text{Var}(\beta_k)})]$$

- For exploratory purposes, the incidence rate over the entire follow-up period will be calculated using the person-year method by treatment arm as follows.

- 1) Calculate the number of events and person-year at risk by treatment arm.
- 2) Calculate the incidence rates and its corresponding 95% CI by treatment arm. (1 year is calculated as 365.25 days)

$$\text{Rate} = \frac{\text{Number of events}}{\text{Person - year}}$$

95% CI:

$$[\text{Rate} / \exp(1.96 * \sqrt{\frac{1}{\text{Number of events}}}), \text{Rate} * \exp(1.96 * \sqrt{\frac{1}{\text{Number of events}}})]$$

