Individual subject trial completion date	The day of the completion examination at 11-17 days after the end of the 2-year IMP administration period
Individual subject trial period	The period from the day of obtaining the subject's informed consent to the day of trial completion or the day of the withdrawal examination. Does not include the follow-up period nor the outcome survey.

1 Introduction

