3.2 Rationale for Trial Design

In this trial, the primary endpoint is DFS defined as the time from randomization to AML relapse or death from any cause, whichever comes first within the observation period. This endpoint was set to assess the efficacy of OCV-501 as a maintenance therapy in AML patients who were judged to have achieved CR following an induction regimen. Since DFS is a time-to-event variable, this trial was designed as a randomized comparative study with two treatment arms (the OCV-501 arm and the placebo-control arm). No DLTs were reported and the tolerability of OCV-501 treatment up to a dose of 3 mg was confirmed, and OCV-501 specific DTH was observed at each dose in this phase 1 trial (Trial 311-10-001), and the number of AML patients is not very high. The maximum dose (OCV-501 3 mg) that has been confirmed safe in the phase 1 trials will be used to assess the efficacy and safety of OCV-501 compared with placebo. Since no treatments are administered in patients who complete consolidation therapy, placebo was set as a control.

The DFS rates in maintenance therapy with other drugs^{25,26,27} in AML patients 60 years or older are summarized below. As DFS rates were approximately 10 to 30% after 2 years, approximately 70 to 90% of events could be observed within 2 years. Thus, the observation period of DFS in this trial is set from the time of randomization to 2 years after the first IMP administration.

Disease Free Survival Rates			
Publication	1 year later	2 years later	3 years later
Cancer and Leukemia Group B Study 9720 (2008) ²⁵	29%	10%	5%
Hellstrand et al (2008) ^{26,*}	44%	32%	27%
Cancer and Leukemia Group B study 9420 (2002) ^{27,**}	40%	20%	18%
Note: values are round number			
*Leukemia-free survival: Definition is identical to DFS. Values are estimated by comparing data among all patients and patients less than 60 years of age.			
** Results of Interleukin 2 monotherapy			

Protocol No. 311-12-001

For overall survival (OS), the cutoff date was set as the date after 728 days (2 years) from the day that the last subject started IMP administration

As mentioned above, no DLTs were reported and the tolerability of OCV-501 treatment up to a dose of 3 mg was confirmed, and OCV-501 specific DTH was observed at each dose in the phase 1 trial. This study will consist of two arms (ie, OCV-501 arm and placebo arm) with consideration of feasibility of patient enrollment.

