11.3.1.1 Primary Endpoint

1) Definition

- Disease-free survival (DFS)
 - Observation period: For each subject, the time from randomization to the DFS-cutoff date. The DFS-cutoff date was set as the completion date of each subject.
 - Definition: The time from randomization until relapse or death from any cause, whichever comes first by the DFS-cutoff date.
 - Event: Relapse or death from any cause by the DFS- cutoff date.
 - Censoring:
 - If an event has not been observed by the DFS-cutoff date, then the last confirmed non-relapse date will be used as the censoring date.
 - For subjects who have withdrawn from this trial before the completion date for reasons other than relapses or deaths, if non-relapse has been confirmed on the withdrawal date, then the withdrawal date will be used as the censoring date.

2) Analysis Set

FAS, PPS

3) Analysis Method

Primary method: Kaplan-Meier curve, log-rank test

The Kaplan-Meier method will be carried out to estimate DFS functions and plot the DFS curve by treatment arm.

- The log-rank test will be used to determine whether there are differences at the 5% significance level in DFS between the OCV-501 treatment arm and the placebo arm.
- The hazard ratio (OCV-501 vs. placebo) and its 95% confidence interval will be calculated using the wald test.
- The 2-year survival rate and median survival time will be calculated and 95% CI of survival rate will be calculated using the Greenwood formula.

Exploratory method:

- Harrington-Fleming Test: applying the weight $1-S(t)$, where $S(t)$ is calculated from Kaplan Meier survival estimate.
- HR and its 95% CI will be calculated at every 3-month interval. The hazard rate will be calculated using the person-year method by treatment arm.
- The Cox PH (Proportional Hazards) model will be used to adjust treatment comparison for a set of covariates which are set to be country (each country) and age (60 to 64 years, 65 to 70 years, and ≥ 71 years) on the time-to-event variable. Also, the assumption that the hazard ratio is constant over time will be graphically assessed by looking at the log-minus-log survival plots with stratification of covariates.

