4.2 General Presentation Considerations

The important terms will be defined as follows:

Term	Definition
Screen failure	A screen failure is a subject from whom written informed consent was obtained, but to whom an IMP was not allocated
Individual subject trial start date	The day of obtaining the subject's written informed consent
Individual subject withdrawal	A subject who discontinue OCV-501 or placebo treatment before completion of the post-treatment observation period
Individual subject trial withdrawal date	The day of the withdrawal examination of the post-treatment observation period within 7 days after the investigator or subinvestigator judged withdrawal to be necessary
Individual subject completion	A subject who complete 2 years of treatment with OCV-501 or placebo, and complete the post-treatment examination at 11-17 days after the end of IMP administration
Individual subject trial completion date	The day of the completion examination at 11-17 days after the end of the 2-year IMP administration period
Individual subject trial period	The period from the day of obtaining the subject's informed consent to the day of trial completion or the day of the withdrawal examination. Does not include the follow-up period nor the outcome survey.

Continuous data will be summarized in terms of the mean, standard deviation (SD), median, minimum, maximum and number of observations, unless otherwise stated. The minimum and maximum will be reported to the same number of decimal places as the raw data recorded in the database. The mean, median, lower quartile and upper quartile will be reported to one more decimal place than the raw data recorded in the database. The SD will be reported to two more decimal places than the raw data recorded in the database. In general, the maximum number of decimal places reported shall be four for any summary statistic.

Categorical data will be summarized in terms of the number of subjects providing data at the relevant time point, frequency counts and percentages. Percentages will be presented to one decimal place. Percentages will not be presented for zero counts. Percentages will be calculated using the number of observations with non-missing values as the denominator.

Changes from baseline in categorical data will be summarized using shift tables where appropriate.

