4.7.3 Reference Efficacy Endpoint

4.7.3.1 DFS until OS cutoff date

1) Definition:

- Observation period: For all subjects, the time from randomization to OS cutoff date
- DFS for reference: The time from randomization until relapse or death from any cause, whichever comes first, by the OS cutoff date
- Event:
Relapse or death from any cause, whichever comes first by the OS cutoff date
- Censoring:
 - If an event has not been observed by the OS cutoff date, the last confirmed non-relapse date will be used as the censoring date.
 - For subjects who have withdrawn from this trial before the OS cutoff date for reasons other than relapse or death, if non-relapse has been confirmed on the withdrawal date, then the withdrawal date will be used as the censoring date. Otherwise, the last confirmed non-relapse date will be used as the censoring date.

2) Analysis Set:

For the judgment of relapse by trial site, DFS will only be evaluated in the FAS.

3) Analysis Method:

The same analysis method will be conducted as for DFS.

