4.13 Changes in the Conduct of the Study or Planned Analysis

Any changes made after the database lock will be recorded in the relevant section of the clinical study report.

Changes from the analysis planned in the protocol are as follows:

Section number	Contents of changes	Reason of changes
4.5 Demographics and Other Basic Characteristics	WT1 mRNA level at Day 1 was added instead of AML diagnosis or at the time of induction therapy or consolidation therapy.	Day 1 data would be more influential than the data at diagnosis or at the time of induction or consolidation therapy.
4.7.1.1 DFS 4.7.2.1 OS	Proportionality assumption will be tested first. Cox PH model will be conducted on every 3 month interval as an alternative analysis.	If proportionality assumption fails, then Cox PH model might be considered invalid to conduct on the whole period.

Section number	Contents of changes	Reason of changes
4.7.1.1 DFS 4.7.2.1 OS	Age, country and other factor (WT1 mRNA) will be adjusted as covariates in the Cox PH model. Furthermore, subgroup analysis will be conducted.	Cox PH model analyses adjusted by covariates are added to investigate the influence of covariates. And the subgroup analyses are added as supplementary analyses.
4.7.2.2 QOL	Mixed-effect model repeated measures will be conducted.	To make a comparison on QOL between two treatment arms.
4.7.2.3 PS	Improvement factor will be created and Wilcoxon 2-sample test will be conducted.	To make a comparison on PS between two treatment arms.
4.7.3. Reference efficacy endpoint 4.7.3.1 DFS until OS cutoff date 4.7.3.2 Therapeutic Response	New efficacy variables have been added.	For the purpose of reference
4.8.2 Adverse Events	A summary of SAEs by severity is not conducted.	Listing will cover it.
4.10 Exploratory Items Analysis	For WT1 mRNA item, t-test is not conducted.	According to the nature of WT1mRNA data, comparison between treatment arms will not be necessary.
4.11 Subgroup analysis	Safety and immune response have been added to the subgroup analysis.	For the purpose of reference

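### Primary DFS is cut off when a subject stops treatment, although Protocol 3.2 observes it to 2 years, and no planned DFS analysis clearly counts the later relapses and deaths that are collected

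*SAP*

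**What the plan says.** - **Protocol 3.2** sets the window by calendar time: "the observation period of DFS in this trial is set from the time of randomization to 2 years after the first IMP administration". Its reason is that about 70 to 90% of events should be seen within 2 years. It says nothing about ending observation when treatment stops.
- **Protocol 11.3.1.1** uses a different cutoff: "The DFS-cutoff date was set as the completion date of each subject". The definitions table gives the completion date as "The day of the completion examination at 11-17 days after the end of the 2-year IMP administration period", so it exists only for subjects who finish treatment. Subjects who withdraw without having relapsed or died fall under a separate censoring rule: "if non-relapse has been confirmed on the withdrawal date, then the withdrawal date will be used as the censoring date".
- **SAP 4.7.1.1** keeps that censoring rule and moves the cutoff itself: "The DFS-cutoff date was set as the completion/discontinuation date of each subject".
- **SAP 4.2**, like the Protocol's definitions, describes withdrawal as "A subject who discontinue OCV-501 or placebo treatment before completion of the post-treatment observation period". It is about stopping treatment, not about withdrawing consent.
- **Protocol 7.1.6.1 and 7.1.6.2** survey survival in all patients, and relapse dates in patients who had not relapsed by the post-treatment period, up to the OS cutoff.
- **SAP 4.7.3.1**, the reference endpoint, has as its observation period "For all subjects, the time from randomization to OS cutoff date" and counts events to that date. Its second censoring rule nevertheless returns withdrawn subjects to the withdrawal date.
- **SAP 4.13** opens its table with "Changes from the analysis planned in the protocol are as follows". The new cutoff wording is not in it.

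**The concern.** Deaths and relapses that occur after a subject stops treatment, but inside the 2-year window of Protocol 3.2, are collected and then left out of the primary endpoint. That is harmless only if stopping is unrelated to what follows, and the documents give reasons to doubt this. Protocol 6.2.1 and 9.2 require withdrawal for use of a prohibited therapy (including anti-cancer drugs and G-CSF), for adverse events and on investigator judgement. Relapse called by the site also stops treatment, while Protocol 11.3.1 makes central judgement the main criterion. A site relapse that is not confirmed centrally therefore reaches the SAP cutoff without a primary event. At withdrawal, marrow is taken only if blasts appear or blood counts fall to a clinically significant degree (Protocol 7.1.4.2).

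If stopping precedes relapse or death, censoring there loses events and overstates DFS in both arms. If the loss also differs between arms, the hazard ratio and the primary log-rank test are biased. OS is not affected, because it is followed regardless of withdrawal.

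**Working it through.** **1. The rules applied to one subject.** The subject stops treatment early for an adverse event, is relapse-free at the withdrawal examination, and dies before the 2-year point.

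| Rule | Result |
|---|---|
| Protocol 3.2 window | Event at death |
| Protocol 11.3.1.1, cutoff | No completion date exists for this subject |
| Protocol 11.3.1.1, censoring rule | Censored at withdrawal examination |
| SAP 4.7.1.1, cutoff and censoring rule | Censored; the death is past the cutoff |
| SAP 4.7.3.1, event line | Event at death |
| SAP 4.7.3.1, second censoring rule | Censored at withdrawal |

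SAP 4.7.3.1 does count later events in completers. The gap concerns early stoppers.

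**2. The plan's own power.** Inputs (Protocol 11.5, SAP 4.12): 60 per arm, placebo 2-year DFS 20%, OCV-501 35% or 40%, exponential times, two-sided 5% log-rank test. HR is OCV-501 over placebo.

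- HR = ln(p1)/ln(0.20) = 0.652 or 0.569.
- Events with full 2-year follow-up: 60 × (0.80 + 0.65) = 87; 60 × (0.80 + 0.60) = 84.
- Power = Φ(√D/2 × |ln HR| − 1.96) = 51.3% and 73.3%, within 2 points of the stated 53% and 75%.

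This assumes nobody is censored at discontinuation, and the plan shows no allowance for it.

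**3. Stopping unrelated to outcome.** Let d be the 2-year probability of stopping without an event (assumed, equal in both arms) and c = −ln(1 − d)/2. With event hazard λ per year, events per arm = 60 × λ/(λ + c) × (1 − exp(−2(λ + c))).

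| d | Events, HR 0.65 / 0.57 | Power, HR 0.65 / 0.57 |
|---|---|---|
| 0% | 87.0 / 84.0 | 51.3% / 73.3% |
| 10% | 83.5 / 80.6 | 49.7% / 71.5% |
| 20% | 79.9 / 77.1 | 48.0% / 69.6% |
| 40% | 72.0 / 69.4 | 44.1% / 65.0% |

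This costs power without bias. Simulated under no effect, 5% v 20% stopping gives HR 1.00 and type I error 5.3%.

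**4. Stopping shortly before an event.** Simulation, 50,000 trials per scenario, with HR rounded to 0.57 and 0.65. Each event within 2 years is replaced, with probability q, by censoring 2 to 8 weeks earlier. Both q and the lead time are assumptions.

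Equal loss in both arms:

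| q | Power, HR 0.57 | Power, HR 0.65 | Placebo 2-year DFS | Type I error |
|---|---|---|---|---|
| 0% | 72.8% | 52.2% | 20% (assumed) | 5.3% |
| 5% | 71.3% | 50.2% | about 21.5% | 5.3% |
| 10% | 69.1% | 48.1% | 23.2% | 4.9% |
| 20% | 64.2% | 44.6% | 27.1% | 5.1% |

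Check by the formula in step 2 at q = 10%: 84.0 × 0.9 = 75.6 events gives 68.6%; 86.9 × 0.9 = 78.2 events gives 47.8%.

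Unequal loss with no true effect (worst case):

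| Placebo v OCV-501 loss | HR observed | Type I error |
|---|---|---|
| 5% v 10% | 0.95 | 5.9% |
| 5% v 15% | 0.90 | 7.8% |
| 5% v 20% | 0.85 | 11.2% |

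A milder 8% v 12% gives 5.4%, no different from the 5.3% baseline. In the other direction (placebo 15%, OCV-501 5%), a true HR of 0.57 reads 0.63 with power 51.1%, and 0.65 reads 0.72 with power 30.4%.

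**5. Where a 2-year window should end.** Week 103 falls on Days 710 to 720 and the completion examination 11 to 17 days later, so on Day 710 + 11 = 721 to Day 720 + 17 = 737. Two years (728 days) after Day 1 is Day 729. The completion examination carries the scheduled marrow, so a relapse found on Days 730 to 737 would be lost under a strict 2-year limit.

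**The case against.** Protocol 3.2 is rationale text. It explains the length of the window, and a maximum window can coexist with a censoring rule inside it. The Protocol already censored at withdrawal, so the SAP's cutoff wording only tidies a completion date that early stoppers never have. Censoring falls at the withdrawal examination, within 7 days of the decision to withdraw, not at the last dose. Such censoring is a recognisable choice for an exploratory trial of monotherapy, since later events may follow other anti-cancer treatment. The reference endpoint was added to follow all subjects to the OS cutoff, and its awkward censoring rule may be a carry-over meant only for subjects without an event. Blinding with indistinguishable vials, the same Montanide emulsifier in both arms, two-weekly hematology, a smear at withdrawal and central confirmation of no relapse all make a large or unequal loss less likely.

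Much of this stands. The SAP did not create the censoring rule, the unequal-loss scenarios have no support in the documents, and keeping the primary test is defensible. But the Protocol still gives two end points for the same observation period, the changed cutoff is not listed in SAP 4.13, and the one analysis that could use the later events can be read either way. Left open, that reading could be chosen after unblinding.

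**Conclusion.** The concern holds and should be fixed. The contradiction between Protocol 3.2 and the operative definitions, and the one inside SAP 4.7.3.1, rest on the text alone. The size of the effect does not: without a discontinuation rate, neither magnitude nor direction is known. Under equal informative loss of 5 to 20% of events, the cost is about 1.5 to 9 points of power and an overstated DFS in both arms, with no inflation of type I error. Bias in the hazard ratio and the test needs an informative loss that differs between arms. The documents show no such imbalance, and they plan no DFS analysis that would clearly reveal its effect.

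**What to change.** 1. In SAP 4.7.1.1, pre-specify a FAS sensitivity analysis of DFS regardless of discontinuation. Count all deaths and relapses up to the later of 2 years after first dose and the completion examination. Use central judgement where smears exist and the surveyed site date otherwise, and censor at the last date known relapse-free.
2. In SAP 4.7.3.1, delete the second censoring rule, so that events after withdrawal count to the OS cutoff as the event line says.
3. Before unblinding, reconcile Protocol 3.2, Protocol 11.3.1.1 and SAP 4.7.1.1 on one primary observation period, and list the cutoff change in SAP 4.13.
4. Extend the disposition summaries in SAP 4.3.1 to show discontinuations without relapse by arm, reason and time.

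The cost is wording and one added analysis on data already collected, with no new visits. Items 1 and 2 overlap but answer different questions: one keeps the 2-year horizon of the primary analysis, the other runs to the OS cutoff on site judgement.

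The limits should be stated. Relapses after withdrawal are not centrally reviewed, because smear collection ends with the post-treatment period. They have no fixed assessment interval and may follow other therapy. Later relapse dates may be missing for site-called relapses not confirmed centrally. For these reasons the analysis is proposed as a sensitivity analysis and not as a required replacement of the primary.
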